9.2 Discussion of Study Design, Including Choice of Control Group

Study 270-301 is designed to be a Phase 3, single-arm, open-label study in hemophilia A patients with residual FVIII levels ≤ 1 IU/dL previously treated with prophylactic exogenous FVIII. Hemophilia A patients who provide written informed consent, meet the entry criteria definition of residual FVIII activity, have well-documented historical data for the previous 12 months concerning exogenous FVIII usage and bleeding episodes, and do not have antibodies to AAV5 will be eligible to enroll in the study.

Approximately 130 subjects will be enrolled at the 6E13 vg/kg BMN 270 dose. Subjects will be followed for 52 weeks post-BMN 270 infusion during which safety and efficacy assessments will be taken. After the final analysis at 52 weeks post-infusion, safety and efficacy will then continue to be assessed long-term for approximately a total of 5 years. During enrollment, the DMC will review available safety and efficacy data on an ongoing basis and may decide to recommend dosing subjects at a different dose level (not to exceed 6E13 vg/kg) based on emerging data from 270-301 and their overall benefit:risk assessment.

Study 270-301 is a self-controlled study. Parameters for each subject will be compared to a pre-treatment assessment of safety (liver function) and efficacy (number of bleeds, use of FVIII replacement therapy).

9.3 Selection of Study Population

Approximately 130 adult hemophilia A patients with residual FVIII levels \leq 1 IU/dL may enroll into the study.

Additional criteria for participation in the study are provided in Section 9.3.1 and Section 9.3.2.

9.3.1 Inclusion Criteria

Individuals eligible to participate in this study must meet all of the following inclusion criteria:

- 1. Males \geq 18 years of age with hemophilia A and residual FVIII levels \leq 1 IU/dL as evidenced by medical history, at the time of signing the informed consent.
- 2. Must have been on prophylactic FVIII replacement therapy for at least 12 months prior to study entry. High-quality, well-documented historical data concerning bleeding episodes and FVIII usage over the previous 12 months must be available.
- 3. Treated/exposed to FVIII concentrates or cryoprecipitate for a minimum of 150 exposure days (EDs).

- 4. Willing and able to provide written, signed informed consent after the nature of the study has been explained and prior to any study-related procedures.
- 5. No previous documented history of a detectable FVIII inhibitor, and results from a Bethesda assay or Bethesda assay with Nijmegen modification of less than 0.6 Bethesda Units (BU) (or less than 1.0 BU for laboratories with a historical lower sensitivity cutoff for inhibitor detection of 1.0 BU) on 2 consecutive occasions at least one week apart within the past 12 months (at least one of which should be tested at the central laboratory).
- 6. Sexually active participants must agree to use an acceptable method of effective contraception, either double-barrier contraception (ie, condom + diaphragm; or condom or diaphragm + spermicidal gel or foam) or their female partner either using hormonal contraceptives or having an intrauterine device. Participants must agree to contraception use for at least 12 weeks post-infusion; after 12 weeks, subjects may stop contraception use only if they have had 3 consecutive semen samples with viral vector DNA below the limit of detection.
- 7. Willing to abstain from alcohol consumption for at least the first 52 weeks following BMN 270 infusion.

9.3.2 Exclusion Criteria

Individuals who meet any of the following exclusion criteria will not be eligible to participate in the study:

- 1. Detectable pre-existing antibodies to the AAV5 capsid.
- 2. Any evidence of active infection or any immunosuppressive disorder, including HIV infection.
- 3. Significant liver dysfunction with any of the following abnormal laboratory results:
 - ALT (alanine aminotransferase) > 1.25x ULN;
 - AST (aspartate aminotransferase) > 1.25x ULN;
 - GGT (gamma-glutamyltransferase) > 1.25x ULN;
 - Total bilirubin > 1.25x ULN;
 - Alkaline phosphatase > 1.25x ULN; or
 - INR (international normalized ratio) ≥ 1.4 .

Subjects whose liver laboratory assessments fall outside of these ranges may undergo repeat testing of the entire liver test panel within the same Screening window and, if eligibility criteria are met on retest, may be enrolled after confirmation by the Medical Monitor.

- 4. Prior liver biopsy showing significant fibrosis of 3 or 4 as rated on a scale of 0-4 on the Batts-Ludwig (Batts, 1995) or METAVIR (Bedossa, 1996) scoring systems, or an equivalent grade of fibrosis if an alternative scale is used.
- 5. Evidence of any bleeding disorder not related to hemophilia A.
- 6. Platelet count of $< 100 \times 10^9/L$.
- 7. Creatinine $\geq 1.5 \text{ mg/dL}$.
- 8. Liver cirrhosis of any etiology as assessed by liver ultrasound.
- 9. Chronic or active hepatitis B as evidenced by positive serology testing (HBsAg, HBsAb, and HBcAb) and confirmatory HBV DNA testing. Refer to the Centers for Disease Control (CDC) table for the interpretation of serological test results in the Laboratory Manual.
- 10. Active Hepatitis C as evidenced by detectable HCV RNA or currently on antiviral therapy.
- 11. Active malignancy, except non-melanoma skin cancer.
- 12. History of hepatic malignancy.
- 13. History of arterial or venous thromboembolic events (eg, deep vein thrombosis, non-hemorrhagic stroke, pulmonary embolism, myocardial infarction, arterial embolus), with the exception of catheter-associated thrombosis for which anti-thrombotic treatment is not currently ongoing.
- 14. Known inherited or acquired thrombophilia, including conditions associated with increased thromboembolic risk, such as atrial fibrillation.
- 15. Treatment with any investigational product within 30 days or 5 half-lives of the investigational product prior to the screening period. For subjects who have received a prior investigational product, all ongoing adverse events (AEs) experienced while receiving that investigational product must have resolved prior to screening for this study.
- 16. Any condition that, in the opinion of the Investigator or Sponsor would prevent the patient from fully complying with the requirements of the study (including possible corticosteroid treatment outlined in the protocol) and/or would impact or interfere with evaluation and interpretation of subject safety or efficacy result.
- 17. Prior treatment with any vector or gene transfer agent.
- 18. Major surgery planned in the 52-week period following the infusion with BMN 270.
- 19. Use of systemic immunosuppressive agents, not including corticosteroids, or live vaccines within 30 days before the BMN 270 infusion.

- 20. Concurrent enrollment in another clinical study, unless it is an observational (non-interventional) clinical study that does not interfere with the requirements of the current protocol or have the potential to impact the evaluation of efficacy and safety of BMN 270 and with prior consultation with the Medical Monitor.
- 21. Known allergy or hypersensitivity to BMN 270 investigational product formulation.
- 22. Unwilling to receive blood or blood products for treatment of an adverse event and/or a bleeding episode.

9.3.2.1 Optional Liver Biopsy Inclusion and Exclusion Criteria

Individuals eligible for the optional liver biopsy must meet the following inclusion criterion:

- 1. Able to sign informed consent and comply with requirements for the optional liver biopsy
- 2. Documentation of FVIII activity ≥ 50 IU/dL (or higher, depending on local guidelines and/or Investigator discretion) within 24 hours prior to the liver biopsy being performed (FVIII activity levels should be assessed at the local laboratory). Subjects may be treated with additional exogenous FVIII replacement products in order to increase their FVIII levels activity to an appropriate level, under the supervision/instruction of the Investigator.

Individuals who meet any of the following exclusion criteria will not be eligible for the optional liver biopsy:

1. Any condition that, in the opinion of the Investigator or a hepatologist/radiologist would make liver biopsy contraindicated. This includes (but is not limited to) abnormalities detected on liver ultrasound performed within 28 days of procedure, or prior liver ultrasound result within 90 days that would preclude safe performance of the biopsy.

9.3.3 Removal of Subjects from Treatment or Assessment

Subjects may withdraw their consent to participate in the study at any time without prejudice. The Investigator must withdraw from the study any subject who requests to be withdrawn. Such subjects will always be asked about the reason(s) for withdrawal. The Investigator will discuss with the subject appropriate procedures for withdrawal from the study.

The Investigator should ask the subject's consent to perform the procedures listed under the early termination visit. Should a subject withdraw from the study, all efforts will be made to complete and report the observations as thoroughly as possible up to the date of the withdrawal.

A subject's participation in the study may be discontinued at any time at the discretion of BioMarin or of the Investigator and in accordance with his/her clinical judgment. When

possible, the tests and evaluations listed for the termination visit should be carried out and every effort will be made to gather follow-up safety data if possible.

BioMarin must be notified of all subject withdrawals as soon as possible. BioMarin also reserves the right to discontinue the study at any time for either clinical or administrative reasons and to discontinue participation by an individual Investigator or site for poor enrollment or noncompliance.

Reasons for which the Investigator or BioMarin may withdraw a subject from the study include, but are not limited to, the following:

- Subject requires medication or medical procedure prohibited by the protocol
- Subject does not adhere to study requirements specified in the protocol
- Subject was erroneously enrolled into the study or does not meet entry criteria and not yet been dosed with BMN 270; subjects who do not meet entry criteria but who erroneously receive BMN 270 should remain in the study for safety monitoring
- Subject is lost to follow-up

If a subject fails to return for scheduled visits, a documented effort must be made to determine the reason. If the subject cannot be reached by telephone, a certified letter should be sent to the subject requesting contact with the Investigator. This information should be recorded in the study records.

Subjects may be considered lost to follow-up if the subject has missed 3 consecutive visits in the study and has failed to communicate a reason for this to the site. In addition, the site has documented at least 4 attempted contacts by key research personnel to reach the subject without success in the following manner:

- 2 attempts by telephone or email (if possible); then
- If telephone/email contacts are unsuccessful, 2 attempts must be made by certified letter or by appropriate local process.

Where communication has been made by phone, this should be documented in the subject source notes.

The Investigator or designee must explain to each subject, before enrollment into the study, that for evaluation of study results, the subject's protected health information obtained during the study may be shared with the study Sponsor, regulatory agencies, and IRB/IEC/REB. It is the Investigator's (or designee's) responsibility to obtain written permission to use protected health information per country-specific regulations, such as the Health Insurance Portability and Accountability Act (HIPAA) in the US, from each subject. If permission to use protected

health information is withdrawn, it is the Investigator's responsibility to obtain a written request, to ensure that no further data will be collected from the subject and the subject will be removed from the study.

9.3.3.1 Study Safety Evaluation Criteria

If any of the following events occur in a subject in the study who has received BMN 270 infusion, an urgent evaluation by the DMC will be required and further enrollment into the trial will be temporarily put on hold if recommended by the DMC per Section 9.1.

- 1. Liver dysfunction (criteria do not apply to ALT elevations with an extra-hepatic etiology):
 - \circ ALT > 5x ULN, for more than 2 weeks
 - \circ ALT > 3x ULN and (total bilirubin > 2x ULN or INR >1.5)
 - \circ ALT > 3x ULN with signs and symptoms of liver dysfunction
- 2. The occurrence of Grade 4 or Grade 5 adverse events assessed as related to study drug (events of liver dysfunction are defined above).
- 3. The occurrence of an AE of hepatic failure.
- 4. The detection of high-titer neutralizing antibodies (>5 BU) to hFVIII following BMN 270 infusion in two subjects.
- 5. The occurrence of any cancer (except non-melanoma skin cancer) at any point after BMN 270 infusion.
- 6. The occurrence of a thromboembolic event with FVIII activity > 150 IU/dL in one subject.

If any of the following events occurs in a subject in the study who has received BMN 270 infusion, an urgent evaluation by the DMC will be required. Further enrollment into the trial will continue while DMC evaluation is ongoing, unless deemed otherwise by the DMC:

- 1. The detection of high-titer neutralizing antibodies (>5 BU) to hFVIII following BMN 270 infusion in one subject.
- 2. Occurrence of a thromboembolic event in one subject.

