9 INVESTIGATIONAL PLAN

9.1 Overall Study Design and Plan

This is a Phase 3, single-arm, open-label study in hemophilia A patients with residual FVIII levels ≤ 1 IU/dL treated continuously with prophylactic exogenous FVIII for a minimum of one year prior to enrollment. Subjects will be enrolled at approximately 60 sites worldwide. Subjects must have high-quality, well-documented historical data available concerning previous bleeding episodes and exogenous FVIII usage over the previous 12 months in order to be eligible to enroll in the study.

Approximately 130 adult subjects with severe HA will receive a 6E13 vg/kg dose of BMN 270 as a single intravenous infusion. Approximately 20 subjects will enroll in the study with at least 12 months of well-documented high-quality historical data concerning previous bleeding episodes and exogenous FVIII usage, while approximately 110 subjects will enroll in the study after having completed approximately 6 months' participation in the BioMarin-sponsored non-interventional study 270-902, in which bleeding and FVIII use data prior to gene therapy will be prospectively collected.

In order to minimize bias in the ongoing study and to assure safe and ethical conduct of the clinical trial, an independent Data Monitoring Committee (DMC), consisting of experts in clinical trials, statistics, and hemophilia, has been convened. The DMC will have sole access during the trial to amalgamated FVIII activity levels, FVIII usage, and bleeding data and will review available safety and efficacy (eg, FVIII activity) data during the study on an ongoing basis; they may determine, based on emerging data and the risk/benefit profile, that further enrollment at 6E13 vg/kg should be discontinued in favor of a different dose of BMN 270, not to exceed 6E13 vg/kg. If the DMC recommends a dosing modification, then additional

subjects may be enrolled, up to a total of approximately 130 subjects, at the new BMN 270 dose level (regardless of the number of subjects previously enrolled at 6E13 vg/kg).

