There will be an ongoing review of individual subject safety by the Medical Monitor, and both safety and efficacy data by the DMC. Therapeutic oral corticosteroids or other

immunosuppressive agents may be initiated when a subject's ALT values are elevated, and subsequent dosage adjustments made, after consultation between the Investigator and the Medical Monitor. Management of ALT elevations is discussed in more detail in Section 9.7.8.3.

Any safety signal may trigger a review of the data and possible additional immunogenicity studies or other diagnostics deemed necessary that include an assessment of cellular immune responses using collected peripheral blood mononuclear cells (PBMCs).

An optional liver biopsy will be performed (in subjects who consent to do so) during Year 1 post-infusion, at or around Week 52, and/or during Years 2-5 following BMN 270 infusion. Subjects who consent to the liver biopsy will have additional assessments, including a liver ultrasound and FibroScan, and will receive prophylactic FVIII prior to the procedure, as indicated in the judgment of the Investigator, to minimize the risk of bleeding.

Schedules of assessments for the Screening and Infusion period (Table 9.1.1), Post-Infusion follow-up periods (Table 9.1.2, Table 9.1.3, Table 9.1.4, Table 9.1.5), during the use of oral corticosteroids (Table 9.1.6), and for the optional liver biopsy (Table 9.1.7) are presented below.

Page 43

Table 9.1.1: Schedule of Events – Screening and Infusion

	Prio	Prior to BMN 270 Infusion								
Assessment	Screening* (Day -28 to Day -1)	Smart Rescreening ⁱ (Day -28 to Day -1)	Baseline (Day -7 to Day -1)h	BMN 270 Infusion Visit (Day 1) ^k						
Informed consent	X									
Demographics (age, sex, race, ethnicity)	X									
Medical History	X									
Physical Examination ^a	X		X	X						
Height and Weight	X									
Vital Signs	X	X	X	X						
Assessment of Adverse Events and Concomitant Medications	X	X	X	X						
Documentation of bleeding episodes and FVIII usage for previous 12 months (by either subject or clinical information)	X	X	X							
Distribution of subject diaries and training in their use ¹	X									
Electrocardiogram	X									
Liver Ultrasound	X									
hFVIII Assays ^b	X	X ^j	X							
AAV5 TAb Assays ^c	X	X	X	X						
AAV5 TI Assay			X							
Screen for Hepatitis B, Hepatitis C, HIV ^d	X									
Blood chemistry, hematology, and coagulation tests ^c	X	X	X							

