9.7.8.3 Liver and Hepatitis Testing

Subjects will be screened for evidence of previous or active hepatitis B or hepatitis C infection at Screening; hepatitis B screening should include HBsAg, HBsAb, and HBcAb. Subjects with documented results showing an absence of active hepatitis B or hepatitis C infection (as measured by positive DNA for hepatitis B or positive RNA testing for hepatitis C) 30 days prior to providing signed informed consent do not need to repeat those tests during the screening period.

Evidence of ongoing hepatitis B or hepatitis C infection is exclusionary. Subjects with a history of hepatitis B or hepatitis C infection prior to study entry will be tested for hepatitis B and hepatitis C reactivation at Week 16. Subjects with a history of hepatitis B or hepatitis C will be asked for information about the treatments received as part of their medical history assessment at Screening.

Subjects with a previous history of hepatitis B or hepatitis C who receive therapeutic oral corticosteroids prior to Week 16 do not need to complete the Week 16 reactivation assessment; instead, they will be tested for hepatitis B and hepatitis C reactivation at the time points listed in Table 9.1.6.

A liver ultrasound and liver tests (LTs) during Screening will identify any significant hepatic dysfunction.

LTs will be monitored on a regular basis; at each time point, the following LTs should be assessed:

Table 9.7.8.3.1: Liver Tests

Liver Tests (LTs)								
Alkaline Phosphatase	AST (SGOT)	Total Bilirubin	LDH					
ALT (SGPT)	Direct Bilirubin	GGT						

ALT, alanine aminotransferase; AST, aspartate aminotransferase; GGT, gamma-glutamyltransferase; LDH, lactate dehydrogenase; SGOT, serum glutamic-oxaloacetic transaminase; SGPT, serum glutamic-pyruvic transaminase

Elevated ALT levels (above the upper limit of normal range) should be evaluated according to the following plan (note that these evaluations may indicate additional testing of LTs and FVIII levels at unscheduled visits; these unscheduled laboratory tests may be completed by a mobile nursing professional at sites where the use of MN services has been approved):

Table 9.7.8.3.2: Evaluation of ALT Elevations

ALT Level	Work-Up
≥1.5x Baseline	 Continue to monitor LTs and FVIII per protocol (repeat within 7 days if next protocol scheduled visit is >7 days from the time of the reported ALT elevation)

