10.2.1 Events of Special Interest (EOSI)

The following EOSI need to be reported to the Sponsor within 24 hours of site awareness, irrespective of seriousness, severity or causality:

- Elevation of ALT > ULN or $\ge 1.5x$ baseline value, regardless of whether that elevation triggers an initiation or modification of oral corticosteroid treatment
- Events potentially meeting the criteria for Hy's law (ALT or AST elevation $\geq 3x$ ULN plus total bilirubin $\geq 2x$ ULN)
- Thromboembolic event
- Systemic hypersensitivity, anaphylactic, or anaphylactoid reactions (refer to Appendix 1)
- Development of anti-FVIII inhibitory antibodies (inhibitors)

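### The liver trigger for urgent DMC evaluation (Section 9.3.3.1, criterion 1) names ALT only, so an AST-led potential Hy's law case meets none of its bullets

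*Protocol*

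**What the plan says.** All references are to Protocol Amendment 6 unless noted.

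- **Section 9.3.3.1, criterion 1** has three bullets. The first is ALT above 5x ULN for more than 2 weeks. The second is "ALT > 3x ULN and (total bilirubin > 2x ULN or INR >1.5". The third is ALT above 3x ULN with clinical evidence of liver dysfunction. The heading adds that the "criteria do not apply to ALT elevations with an extra-hepatic etiology". Meeting any criterion in this list obliges an urgent DMC evaluation, with an enrolment hold if the DMC recommends one.
- **Section 9.3.3.1, criteria 2 and 3** are the other urgent routes a liver case could take: "The occurrence of Grade 4 or Grade 5 adverse events assessed as related to study drug" and "The occurrence of an AE of hepatic failure". Criterion 2 carries a parenthesis saying that liver dysfunction events are those defined in criterion 1.
- **Section 10.2.1** lists, for reporting to the sponsor within 24 hours, "Events potentially meeting the criteria for Hy's law (ALT or AST elevation" of at least 3x ULN together with total bilirubin of at least 2x ULN.
- **Table 9.7.8.3.2** uses the same ALT-or-AST pattern as the prompt for albumin and PT/INR.
- **Section 9.1** says the DMC "will review available safety and efficacy (eg, FVIII activity) data during the study on an ongoing basis" and that "Any safety signal may trigger a review of the data".

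**The concern.** Amendment 6 (summary of changes, item 11) introduced the Hy's law event on the ground that it combines aminotransferase and bilirubin elevations. The event list and the ALT work-up table were written with AST included. Criterion 1 still reads as it did in Amendment 4.

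A case that the protocol itself labels potential Hy's law therefore gets a mandatory urgent DMC evaluation when ALT leads, but not necessarily when AST leads. This is a liver-directed product, and under Section 9.3.5 subjects are followed for 52 + 208 = 260 weeks after infusion, so the trigger list still has work to do after enrolment closes.

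**Working it through.** There is no figure in the plan to reproduce. The check is a comparison of two rules. ALT, AST and total bilirubin (TB) are in multiples of ULN.

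**Rules as written**

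- Section 10.2.1: E = (ALT ≥ 3 or AST ≥ 3) and TB ≥ 2.
- Section 9.3.3.1, criterion 1: C1 = (ALT > 5 for > 2 weeks) or (ALT > 3 and (TB > 2 or INR > 1.5)) or (ALT > 3 with signs and symptoms).

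**Reasoning.** Every arm of C1 implies ALT > 3. If ALT ≤ 3, C1 is false whatever the AST, bilirubin, INR or symptoms. E is true with ALT ≤ 3 whenever AST ≥ 3 and TB ≥ 2. The whole region ALT ≤ 3, AST ≥ 3, TB ≥ 2 is thus reportable but outside criterion 1.

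**Worked cases**

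| ALT | AST | TB | INR | Symptoms | Section 10.2.1 event | Criterion 1 |
|---|---|---|---|---|---|---|
| 2.9 | 6.0 | 2.5 | 1.2 | no | yes | no |
| 2.0 | 3.5 | 2.2 | 1.2 | no | yes | no |
| 1.0 | 4.0 | 2.5 | 1.2 | no | yes | no |
| 2.0 | 6.0 | 3.0 | 1.6 | yes | yes | no |
| 3.5 | 4.0 | 2.5 | 1.2 | no | yes | yes |
| 4.0 | 2.0 | 2.0 | 1.0 | no | yes | no |

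The fourth row shows that raised INR and symptoms do not rescue an AST-led case. The last row is a lesser mismatch: criterion 1 uses strict inequalities where Section 10.2.1 does not, so exact-boundary values also drop out.

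**Coarse grid.** Of 720 AST-led combinations (ALT ≤ 3, AST ≥ 3, TB ≥ 2, with INR, duration and symptoms varied), all 720 met E and 0 met C1.

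**Fine grid.** ALT and AST ran from 0.5 to 8.0 and TB from 0.5 to 5.0, all in steps of 0.1. INR was 1.0 or 1.6, symptoms yes or no, and duration over 2 weeks yes or no when ALT > 5. Combinations with E true and C1 false:

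- AST-led: 26 ALT values × 51 AST values × 31 TB values × 4 (INR by symptoms) = 164,424.
- ALT exactly 3 with AST < 3: 25 AST values × 31 TB values × 4 = 3,100.
- ALT > 3 with TB exactly 2, normal INR, no symptoms, not prolonged: 50 ALT values × 76 AST values = 3,800.
- Total: 164,424 + 3,100 + 3,800 = 171,324, with nothing left over.

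The use of this count is to show that there are only two kinds of missed case: AST-led and exact-boundary. The proportions depend on the grid limits and step and say nothing about how often such cases occur.

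**The case against.** The strongest reply is that the lists have different jobs, that nothing in Section 9.3.3.1 is false, and that little is left for the DMC to decide. Enrolment is complete (Amendment 6 summary, item 1) and each subject receives one infusion, so the enrolment hold has no effect. Item 11 placed Hy's law in expedited reporting and describes it as already monitored through routine pharmacovigilance.

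Existing cover is also wider than the Hy's law event alone. ALT above ULN, or at least 1.5x baseline, is a separate 24-hour event under Section 10.2.1. The first two cases in the table would therefore be reportable on ALT as well. They would also enter the middle row of Table 9.7.8.3.2, with repeat tests within 72 hours, Medical Monitor consultation and further laboratory work-up. Only the third, with ALT at 1.0x ULN, may lack the ALT pathway. The DMC charter and Section 15 of Amendment 6 were not available and could contain further triggers.

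Most of this stands as a limit on the size of the point. It does not close the gap:

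- The Section 10.2.1 report and the work-up lead to the sponsor and the Medical Monitor. Neither section obliges urgent DMC evaluation.
- Ongoing DMC review carries no stated urgency, and signal-triggered review is permissive.
- Criterion 3 needs hepatic failure, a later and worse state than the warning pattern.
- Criterion 2 needs a related Grade 4 or 5 event, and its parenthesis can be read as sending liver events back to the ALT-only list.
- Section 9.3.3.1 treats urgent evaluation and the hold as separate consequences. Its second list requires evaluation while enrolment continues, so completed enrolment removes only the hold.

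**Conclusion.** The point holds as an optional, low-cost safety improvement. Under Section 9.3.3.1, an AST-led case with AST ≥ 3x ULN, bilirubin ≥ 2x ULN and ALT ≤ 3x ULN meets no bullet of criterion 1. It requires urgent DMC evaluation only if it also qualifies under criterion 2 or 3.

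The expected frequency is low: item 11 of the Amendment 6 summary records no Hy's law event in any BMN 270 study. No efficacy result, sample size or error rate depends on it. The conclusion is confined to Section 9.3.3.1 as written, and rests on the assumption that the charter and Section 15 of Amendment 6 do not already add an AST-inclusive trigger.

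**What to change.** Keep the three existing bullets and add a fourth to criterion 1: ALT or AST ≥ 3x ULN plus total bilirubin ≥ 2x ULN (potential Hy's law, as in Section 10.2.1). Extend the extra-hepatic exclusion from ALT elevations to ALT or AST elevations, so that AST rises from non-liver sources do not trigger it.

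On the fine grid this leaves no Section 10.2.1 Hy's law combination outside criterion 1 and adds no trigger beyond that definition. It also removes the boundary mismatch. The bilirubin arm of the second bullet becomes redundant, which is harmless and can be tidied at the same time. Adding AST to the INR arm as well is not advised. It would create triggers outside the Hy's law definition, for example ALT 2.0, AST 3.5, bilirubin 1.5 (all x ULN) with INR 1.6.

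The cost is one bullet and one phrase in Section 9.3.3.1, plus the matching line in the DMC charter if it repeats the rule. No new tests are needed, because AST and total bilirubin are in the panel of Table 9.7.8.3.1, for which Section 9.7.8.3 states: "LTs will be monitored on a regular basis; at each time point, the following LTs should be assessed". The downside is possibly a few more ad hoc DMC notifications.
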